4.2 SCIENTIFIC RATIONALE FOR STUDY DESIGN

This study is intended to explore the safety and efficacy of TWB-103 in subjects of diabetic lower limb ulcer. As a pilot study, in order to gain bounty clinical experience with few subjects, it is designed as a single-arm small scale study. Because of the nature of TWB-103, whose cell part is stored at $-70 \sim -80^{\circ}\text{C}$, it will be applied to the wound only at the study site by the investigator. Based on the expectation that diabetic ulcers usually heal slowly even under advanced therapeutic regimen, subjects are scheduled to receive TWB-103 treatment once a week for up to 12 applications. A 24-week follow-up is also required to observe long-term safety and to further evaluate the wound healing status.

4.3 JUSTIFICATION FOR DOSE

The current cell density in each mL of prepared TWB-103 is 600,000 cells/mL. In the nude rate study, 0.2 mL of TWB-103 which contained 120,000 cells was applied to each excision wound of 12 mm in diameter ($\sim 106,200 \text{ cells/cm}^2$). This dosage was considered as safe because no significant abnormality was observed. In the hyperglycemia porcine wound study, full thickness excision wounds were treated with TWB-103 at 45,000 cells/cm² and 90,000 cells/cm² wound area. No adverse effect was detected. In the ongoing clinical trial donor site wounds have been treated with 0.05 mL of TWB-103 containing 30,000 cells/cm² wound area. Considering that donor site wounds have largely intact dermis in which substantial number of fibroblasts are present while the diabetic ulcers tend to be deficient of functional dermis, the dosage proposed to be used in this study will be 0.15 mL of TWB-103/cm² wound area, that will equal to 90,000 cells/cm² wound area. Furthermore, considering that there are probably 200,000~600,000 fibroblasts/cm² human skin, such dose is thought to be reasonable.

4.4 END OF STUDY DEFINITION

A subject is considered to have completed the study if he or she has completed the End-of-Treatment Visit (for withdrawal during treatment period) or Week 36 (or 24 weeks after the End-of-Treatment Visit) shown in the Schedule of Activities (SOA), Section 1.3. The study is considered completed when all subjects are no longer being examined or the last study visit or procedure shown in the SOA of all subjects of the study site have been performed.

5 STUDY POPULATION

5.1 INCLUSION CRITERIA

In order to be eligible to participate in this study, an individual must meet all of the following criteria:

1. Adults at least 20 years of age.
2. With diagnosed diabetic mellitus (DM), e.g. currently under DM medication treatment, or with HbA1c $\geq 6.5\%$ but $\leq 12\%$, or with fasting plasma glucose ≥ 126 mg/dL (7.0 mmol/L), or with plasma glucose ≥ 200 mg/dL (11.1 mmol/L) in the two-hour 75-gram oral glucose tolerance test (OGTT).
3. With at least one cutaneous ulcer on or below malleoli, and not healing for at least 4 weeks (the ≥ 2 -week standard of care period can be counted as part of the 4-week ulcer history).
4. With ankle brachial index (ABI) ≥ 0.4 on the limb with the study ulcer. For subjects with $0.6 > \text{ABI} \geq 0.4$, the investigator will arrange for providing proper treatment to the subject, such as improving circulation by medication or surgical procedures, etc.
5. The study wound is not prone to infection (the wound can be maintained clean and well bandaged, there is no nearby infected lesion, and there is no history of recurrent infections).
6. The wound should allow complete sealing of the wound by Tegaderm™ film.
7. The study wound size is between 1~33 cm². The wound depth should be at least full-thickness ulcer (penetrating skin). The depth of wound may reach ligament, joint capsule, fascia, or tendon. There should be no sign of osteomyelitis. The wound does not exceed Wagner Grade 2.
8. Under the standard care of Investigator for at least 2 weeks, the study wound has not shown significant healing. Significant healing is defined as the following: The area of healed tissue reaches at least 30% of the area of initially presented wound.
9. When the subject has more than one wound which met the inclusion criteria, only one wound is selected as the study wound. The other wounds will be treated by standard cares.

10. Except hyperglycemia, co-morbidities are under control and non-life threatening as determined by the Investigator based on medical history, physical examination, vital signs, or clinical laboratory tests, etc.
11. A negative pregnancy test at Screening. This applies to any female subject with childbearing potential.
12. Agrees to use acceptable contraceptive methods while on study (from signing informed consent form to the end of the study).

Acceptable contraceptive methods include:

- a. Established use of oral, injected or implanted hormonal methods of contraception
- b. Placement of an intrauterine device (IUD) or intrauterine system (IUS)
- c. Barrier methods of contraception: condom or occlusive cap (diaphragm or cervical/vault caps)

13. Able to follow the Investigator's instruction on wound care.
14. With signed informed consent form.

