1.2 SCHEMA

1.3 SCHEDULE OF ACTIVITIES (SOA)

Visit	Screening ^{1,2}	Treatment ^{3,4}			Follow-up ^{3,5}	Unscheduled ⁶
Visit number	1	2	3~13	14	15~21	-
Week(s) relative to Day 1	Within 4 weeks prior to Day 1 ⁹	Day 1 ⁹	1, 2, 3, 4, 5, 6, 7, 8, 9, 10, 11	12 or End of Treatment	13, 14, 16, 20, 24, 30, 36 or 1, 2, 4, 8, 12, 18, 24 (after End-of-Treatment) ³	-
Target day	-28 ~ 1	-	8, 15, 22, 29, 36, 43, 50, 57, 64, 71, 78 (± 2)	85 (± 2)	92 (± 2), 99 (± 2), 113 (± 3), 141 (± 6), 169 (± 6), 211 (± 6), 253 (± 6) or 7 (± 2), 14 (± 2), 28 (± 3), 56 (± 6), 84 (± 6), 126 (± 6), 168 (± 6) (after End-of-Treatment) ³	-
Obtain signed informed consent	X					
Assign identification number	X					
Obtain demographic characteristics	X					
Medical history	X					
Medication history	X					
Eligibility ⁷	X ⁷	X ^{7,8}				
Physical exam	X	X ⁸	X	X	X	X
Height and Weight	X					
Vital signs	X	X ⁸	X	X	X	X
Pregnancy test (urine or serum) for applicable subjects	X ¹		X ¹⁰	X ^{4,11}		(X)
Laboratory test	X ¹		X ¹⁰	X ^{4,11}		(X)
PRA test: Class I HLA	X ¹			X ^{4,11}		(X)
Ankle Brachial Index	X ¹					
Ulcer evaluation ¹³	X ²	X ⁸	X ⁸	X	X	(X)
Standard of Care ¹²	X ²	X ^{8,14}	X ^{8,14}	X	X	(X)
TWB-103 application		X	X			
Adverse event	X-----X					
Concomitant medications	X-----X					

1. Procedures performed between signing ICF and Day 1 are acceptable. However, procedures should be completed before the TWB-103 application if performed on Day 1; in this case, the same procedures scheduled for Day 1 can be waived.
2. During this screening period, subjects will receive standard-of-care to the target ulcer wound for at least 2 weeks to observe the wound healing rate (inclusion criteria #8). The wound size before and after the standard-of-care treatment should be recorded. The choice of standard-of-care will be at investigator's discretion based on the subject's physical condition.
3. If any subject has confirmed wound closure before week 12, he/she will stop TWB-103 application and complete assessments of End-of-Treatment (Week 12). Those subjects who have confirmed wound closure before week 12 will have follow-up visits at 1 week, 2 weeks, 4 weeks, 8 weeks, 12 weeks, 18 weeks and 24 weeks after the End-of-Treatment Visit.

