Treatment for diabetic foot ulcer varies depending on the cause, the severity and condition of ulcer wound. A good wound cleansing and a moist wound environment, such as daily saline, are common self-care for diabetic foot ulcer. A debridement to remove necrotic or infected tissues can help ulcer healing. Management of wound infection, a serious complication of a foot ulcer, is also typical to prevent the deterioration of the ulcer wound. Evaluation and correction of peripheral arterial insufficiency will increase the circulation and improve the healing of ulcer. Moreover, pressure from walking can make an infection worse and an ulcer expand, particularly for overweight patients, and therefore stay off the feet can prevent pain and ulcers. Patients may benefit from using appropriate therapeutic footwear, such as diabetic shoes, compression wraps and shoe inserts. Surgical intervention may be also suggested by the doctors to alleviate pressure around the ulcer. Many topical over-the-counter treatments are available for foot ulcers, including dressings containing silver or silver sulphadiazine cream, polyhexamethylene biguanide (PHMB) gel or solutions, iodine (either povidone or cadexomer), or medical grade honey in ointment or gel form.

Although there are many standard treatments for diabetic foot ulcer, as described above, diabetic foot ulcer usually results from multiple pathological factors (e.g. vascular insufficiency, altered cellular activity, and a dysfunctional extracellular matrix), leading to a deficient wound bed, which often fails to respond to conventional therapy alone. A multidisciplinary approach is therefore in need in giving better treatment outcomes for diabetic foot ulcer. Cell therapies have shown as a promising solution for diabetic wound healing, owing to the ability of cells to secrete an array of factors that facilitate the wound healing. Particularly, the safety records of clinical use of dermal fibroblasts in wound healing have been superior in the past two decades. Moreover, fibroblast-containing products, including Apligraf®, Demagraft®, have been approved for treating diabetic foot ulcers. TWB-103 which contains cultured fetal dermal fibroblasts is being developed to overcome the deficits associating with the current cell products such as high pricing, lack of donor tissue and short shelf life, *etc.*

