4 STUDY DESIGN

4.1 OVERALL DESIGN

This study is to evaluate if applying TWB-103 on diabetic ulcer wound can speed up the wound healing in subjects with diabetic lower limb ulcer which has not shown healing for at least 4-week duration. This study is designed in a Phase I/II, single-arm manner. This study plans to enroll 10 subjects (including 8 evaluable per-protocol subjects) with diabetic lower limb ulcers for treating with up to 12 weekly applications of TWB-103 and evaluating the safety and efficacy.

Eligibility will be checked during screening and at Day 1 Visit. The potential subjects with diabetic lower limb ulcer will be arranged to receive standard of care only for at least 2 weeks during screening period. The standard of care will be performed at the investigator's discretion based on the condition of each subject. Any subject whose study ulcer size decreases by 30% or more after this standard of care will be excluded from the study.

TWB-103 is applied once a week by the investigator at the study site, starting from Day 1, until wound closure is confirmed or up to 12 weekly applications. An ulcer is considered healed only after closure is confirmed at the visit 2 weeks later. Therefore, a wound closure should be observed at three consecutive visits (i.e. a duration of 2 weeks) for an ulcer to be deemed as healed. For wound closure which is first observed at Week 11 or Week 12, and has a confirmation at Week 13 or Week 14, respectively, will be considered as a healed wound closure within 12 weeks. If any subject has confirmed wound closure before week 12, he/she will stop TWB-103 application and complete assessments of End-of-Treatment (Week 12).

Following the confirmation of wound closure or completion of 12-week treatment period, whichever comes first, subjects will start a 24-week follow-up period. Subjects will have follow-up visits at weeks 13, 14, 16, 20, 24, 30 and 36, if the 12-week treatment period is completed. Those subjects who have confirmed wound closure before week 12 will have follow-up visits at 1 week, 2 weeks, 4 weeks, 8 weeks, 12 weeks, 18 weeks and 24 weeks after the End-of-Treatment Visit.

If the study wound is not closed after TWB-103 treatment, standard of care will be applied during the following 24 weeks of follow-up. If the study wound is healed after TWB-103 treatment, appropriate standard of care should still be applied for protection.

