6.6 PROHIBITED THERAPY/MEDICATION

Prohibited therapy or medication are defined as below:

- Any other investigational drug, device or biological/bioactive treatment during the study period.
- Any treatment/therapy applied to target wound area that may affect the efficacy evaluation of study medication at the investigator's discretion, such as revascularization, hyperbaric oxygen therapy, negative-pressure wound therapy, during TWB-103 treatment period.
- Dressings with anti-microbial activity should not be used for study wounds during TWB-103 treatment period unless approved by sponsor after consultation.
- Antibiotics administered via intravenous injection or intramuscular injection during TWB-103 treatment period.

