6.7 STANDARD OF CARE FOR DIABETIC LOWER LIMB ULCERS

Standard care will be documented in CRF including the type of care (e.g., extent of debridement, use of concomitant medications), timing, and frequency. Parameters for consideration in choosing standard care procedures for diabetic lower limb ulcer include, but not limited, the following:

- Debridement: Removal of necrotic or infected tissue. During TWB-103 treatment period, if judged by the investigator as appropriate, lesser wound debridement is allowed. However, if major surgery is required, the subject should be withdrawn from this study.
- Off-loading: During study period, off-loading devices, such as clutches, wheel chair, off-loading

shoes, etc., may be applied as judged by Investigator.

- Revascularization or other treatment to improve circulation. However, revascularization is prohibited during treatment period (Visit 2~Visit 13).
- Maintenance of a moist wound environment.
- Management of wound infection: If the target wound has low grade infection (\leq Grade 2) during TWB-103 treatment, whether to stop TWB-103 treatment will be judged by the investigator and appropriate treatment to control the infection will be provided at the investigator's discretion. However, if wound is infected ($>$ Grade 2) during TWB-103 treatment or the treatment for the ulcer wound infection requires subject's hospitalization, intravenous infusion or muscular injection of antibiotics, TWB-103 treatment must stop and be replaced by appropriate treatment to control the infection.
- Wound cleansing
- Good blood glucose control: Considering each subject's physical and physiological condition, "good blood glucose control" is defined as blood glucose level as good as possible with the help of physicians. Subjects will have appropriate medication and education to control the blood glucose level. The investigator will also monitor subjects' blood glucose level through the laboratory tests, including fasting glucose and HbA1c test results, collected during this study.

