8.2.2 SCREENING, ELIGIBILITY, AND ENROLLMENT

Screening is defined as the process for identifying a candidate for the study and evaluating their eligibility to participate. Eligibility should be thoroughly checked by the investigators during screening and at Day 1 Visit before the application of TWB-103 based on the inclusion and exclusion criteria. Procedures for screening can be done between signing ICF and Day 1. However, procedures should be completed before

the TWB-103 application if performed on Day 1; in this case, the same procedures scheduled for Day 1 can be waived. The eligibility re-check at Day 1 Visit will be based on the results from Day 1 Visit (vital signs and physical exam) and other information collected during screening. A subject is recognized as enrolled into the study if this subject consented and is screened, with eligibility verified.

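### The 2-week non-healing run-in may precede a revascularization, so perfusion-driven healing can be counted as change under TWB-103

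*Combined protocol and SAP*

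**What the plan says.** Inclusion 8 (protocol 5.1, repeated in the synopsis) asks that "Under the standard care of Investigator for at least 2 weeks, the study wound has not shown significant healing", with significant healing set at 30% of the initial area. Section 4.1 states the same rule as an exclusion: "Any subject whose study ulcer size decreases by 30% or more after this standard of care will be excluded from the study". Footnote 2 of the schedule of activities adds: "The wound size before and after the standard-of-care treatment should be recorded". What the care consists of is left to the investigator (8.2.9).

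Inclusion 4 accepts an ABI down to 0.4. For values of 0.4 to under 0.6, "the investigator will arrange for providing proper treatment to the subject, such as improving circulation by medication or surgical procedures, etc". Section 6.7 lists, as a component of standard care, "Revascularization or other treatment to improve circulation. However, revascularization is prohibited during treatment period (Visit 2~Visit 13". Section 6.6 bars treatments of the target wound that could influence "efficacy evaluation of study medication at the investigator's discretion, such as revascularization, hyperbaric oxygen therapy, negative-pressure wound therapy, during TWB-103 treatment period".

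On Day 1, "The eligibility re-check at Day 1 Visit will be based on the results from Day 1 Visit (vital signs and physical exam", together with other screening information. ABI is scheduled at screening only.

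Baseline is the last value before the first dose (8.1). Change in wound area is tested within the single arm by a one-sample t-test or Wilcoxon signed-rank test, two-sided at 0.05 (9.4.1, 9.4.3).

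**The concern.** The run-in is there to show that the wound does not heal on background care. That only informs the treatment period if the background stays materially the same from the run-in into Day 1. The protocol itself treats perfusion as material: "Evaluation and correction of peripheral arterial insufficiency will increase the circulation and improve the healing of ulcer" (2.1). Section 6.6 treats revascularization, hyperbaric oxygen and negative pressure as able to affect the efficacy evaluation, but bars them only once treatment has started.

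A wound could therefore fail to heal while poorly perfused, be revascularized shortly before Day 1, and enter as non-healing. Its later shrinkage would be read as change under TWB-103, and with no control arm nothing in the data separates the two. Section 4.1 says the study is to evaluate whether TWB-103 speeds healing, so this bears on a stated aim, though not on the primary endpoint.

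**Working it through.** The plan gives no figure to reproduce. The check is first a reading of the rules together, then an illustration of scale.

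**1. Where a revascularization can fall.** Inclusion 4 directs circulation treatment. Sections 6.7 and 8.2.9 and schedule footnote 14 bar revascularization from Visit 2 (Day 1) to Visit 13, and section 7.2 makes receiving or planning a prohibited therapy a withdrawal condition. A procedure meant to help before or during treatment must therefore precede Day 1.

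**2. How late it can be.** Screening lasts up to 28 days (8.3.1) and the run-in at least 14. 28 − 14 = 14 days can remain between a completed run-in and Day 1.

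**3. What the existing rules catch.**
- Procedure early in screening: the before-and-after 30% comparison sees at least part of the response.
- Procedure late in the run-in: the comparison covers mostly the poorly perfused period.
- Procedure after the run-in: the comparison need not cover it.
- In every case, shrinkage before Day 1 enters the re-measured baseline. Shrinkage after Day 1 does not.

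**4. Whether another rule closes the gap.** Inclusion 3 asks for 4 weeks without healing but lets the run-in count towards them. Exclusion 9 concerns investigational and biological or bioactive treatments and names none of the three therapies. Exclusion 10 is a judgement about clinical conditions. The per-protocol definition (9.3) removes prohibited therapy only within the treatment period, so affected subjects stay in that set too.

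**5. Scale for one subject, all rates assumed.** With constant shrinkage r per 2 weeks, the area reduction at week 12 is 1 − (1 − r)^6. Take r = 30% for a wound with restored perfusion, borrowing inclusion 8's limit: 1 − 0.7^6 = 88.2%. That is 88.2/10 = 8.8 points of the mean at n = 10 and 88.2/8 = 11.0 at n = 8. This is a gross share. The net effect depends on the eligible wound it would stand in for:

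| Background r per 2 weeks | Reduction at week 12 | Difference from 88.2% | Mean shift, n = 10 | Mean shift, n = 8 |
|---|---|---|---|---|
| 29% | 87.2% | about 1.0 | 0.1 | 0.1 |
| 20% | 73.8% | 14.4 | 1.4 | 1.8 |
| 10% | 46.9% | 41.4 | 4.1 | 5.2 |
| 0% | 0% | 88.2 | 8.8 | 11.0 |

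For the closure percentage, one subject is 10 points at n = 10 and 12.5 at n = 8.

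**6. Effect on the t-test.** Simulation, 100,000 runs per setting, assuming zero mean change otherwise, SD 30 points and a shift of +40 points in each affected subject. Two-sided rejection at nominal 5%:

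| Affected subjects | n = 10 | n = 8 |
|---|---|---|
| 1 | 4.9% | 4.9% |
| 2 | 7.3% | 7.7% |
| 3 | 12.2% | 13.3% |

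A shift of −20 points, standing for therapy withdrawn at Day 1, moves the mean by −2.0 per affected subject at n = 10 (−20/10) and −2.5 at n = 8 (−20/8).

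**The case against.** The strongest reply is that the gap is narrow and its consequence small. Revascularization belongs to standard care, so a procedure prompted by a low ABI at the start of screening is partly covered by the 30% rule, and gains before Day 1 go into the baseline. Inclusion 4 also allows medication in place of surgery. Nothing shows that even one of 10 subjects would be revascularized late. A wound that the rule already permits, shrinking 29% per 2 weeks, reaches an 87.2% reduction by week 12 without TWB-103, so uncontrolled background healing weakens the test against zero whatever is done here. This is a pilot with no hypothesis (9.1) and a safety primary endpoint.

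All of that stands, and it limits the point. It does not close the late-procedure case, for which no section sets an interval, a repeat ABI or a renewed run-in.

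The negative-pressure and hyperbaric case is weaker still. Neither therapy is named in 6.7. Their use in the run-in rests on that list being open-ended and on the investigator's freedom of choice.

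A reader might infer that the efficacy results will be biased in favour of TWB-103, or that 88.2% measures the bias. The documents support neither. They give no healing rate after revascularization and no expected number of such subjects, and stopping an active therapy at Day 1 would push the result the other way. Nor do they give reason to extend the concern to everything barred in 6.6. Section 6.1.2 foresees antimicrobial substances during screening and handles them by washing them off before dosing, and exclusion 12 keeps out actively infected study wounds.

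**Conclusion.** The concern holds in limited form. The eligibility rules allow a wound to qualify as non-healing on 2 weeks of care that precede a revascularization, and inclusion 4 with the treatment-period ban places such a procedure in screening. If it falls late in the run-in or after it, continued healing from restored perfusion is counted as change from baseline.

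Frequency, net size and net direction cannot be estimated from the documents. On the assumed constant rates, one affected subject shifts the mean area reduction by 0.1 to 8.8 points at n = 10 and 0.1 to 11.0 at n = 8. Under the simulation's assumptions, one affected subject leaves the t-test near its nominal level, and it takes three of 10 to reach about 12%.

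Only the secondary, exploratory efficacy results are affected. The main conclusion rests on the primary endpoint, which is safety (9.3). Severity is minor: a cheap improvement, not a flaw that undermines the study.

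**What to change.** Add one sentence to inclusion 8 (5.1 and its synopsis copy), to the run-in text in the synopsis and 4.1, to schedule footnote 2, and to 8.2.9 and 8.3.1:

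> The 2-week qualifying period must begin after any revascularization of the study limb and after any negative-pressure or hyperbaric oxygen therapy has ended; the 30% rule uses the area measured at the start of this period.

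Do not extend it to antimicrobial dressings or antibiotics. That would restart the clock for care that 6.1.2 expects in screening, and could delay candidates for little gain.

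From data already recorded under 6.5 and 6.7, list each subject's run-in care, any revascularization date and any change in care at Day 1. Keep this descriptive, with no subgroup comparison. The separate SAP announced in 9.4.1 is the natural place and may already hold such a listing.

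The cost is modest. A procedure in the first 14 days of the 28-day window still leaves time for the 2 weeks. Later cases stay longer in screening or are re-screened under 5.3, with a new consent, CRF and screening number. One extra wound tracing may be needed, and some candidates may be lost from a 10-subject recruitment. Revascularization itself is neither barred nor delayed.

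The sentence reduces the confounding without removing it. A wound that responds to perfusion only after more than 2 weeks can still enter, dressings or off-loading may still change at Day 1, and the rule is no substitute for a control arm.
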